
### 10. Subject Confidentiality

The research team will exercise extreme caution with identifiable private information. Patients randomized to the intervention arm will receive text messages from Way to Health. In the patients informed consent, they are instructed and agree by signing the document that they will not disclose personal health information (PHI) on the Way to Health texting platform and only respond to the text

## Effect of a Digital Engagement Strategy on Healthcare Worker Mental Health and Well-being: A Randomized Controlled Trial

message prompts. When patient participants (both control and intervention) text into the Way to Health or complete a survey, the research team will receive email notification immediately. The research team is instructed to review the message within 1-4 hours of delivery, Monday through Friday, 8 am to 5pm. The line will be closed on Saturday and Sunday however patient participants will receive an out of office message if they text in; the messages notes, Thank you for reaching out, we will get back to you when we get back in the office! and a Patient Inquiry Incident is created. An exception to confidentiality is if significant suicidal ideation, is exhibited through text message or via PHQ-9 question 9 or 9 or DSM-5 question 11. PHQ-9, Question 9 asks about thoughts of being better off dead or of hurting oneself in some way over the last two weeks with an associated scale delineating not at all, several days, more than half the days, or nearly every day. The DSM-5, question 11 asks about During the past TWO (2) WEEKS, how much (or how often) have you been bothered by the following problems? Thoughts of actually hurting yourself? with an associated scale delineating None: Not at all; Slight Rare, less than a day or two; Mild: Several days; Moderate: More than half the days; and Severe: Nearly every day. Those indicating any response beyond not at all or none not at all will be triaged to Penn Behavioral Health Corporate Services / EAP. This is the current standard of care and will be the same for both Cobalt and Cobalt plus in this trial. EAP will receive only the participants phone number via email. If EAP logs into Cobalt, a HIPPA compliant platform, they can view the study's participants phone number, first and last name and PHQ-9 score and PHQ-9 question 9 score. In case Penn Behavioral Health Corporate Services / EAP is unable to contact a study participant within the 72-hour period, a research team member will call the study participant and complete the Ask Suicide-Screening Questions (ASQ) and NIMH TOOLKIT: OUTPATIENT Brief Suicide Safety Assessment.

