## Effect of a Digital Engagement Strategy on Healthcare Worker Mental Health and Well-being: A Randomized Controlled Trial

files that leave the firewall will be stripped of all identifiers besides the study ID and individuals will be referred to by their study ID only. The study ID will also be used on all analytical files. Way to Health and REDCap are secure web applications for building and managing online surveys and databases. Privacy of all study data will be maintained by restricting access to the identifiable information only to approved study staff who have received subject confidentiality and privacy training. Study coordinators will access patient contact information from the database to conduct recruitment phone calls. The study coordinator will review the consent script, which will include a description of the voluntary nature of participation, the study procedures, risks and potential benefits in detail. Participants will be told that all information will be kept strictly confidential, except as required by law. Subjects will be provided a copy of the consent document. All efforts will be made by study staff to ensure subject privacy. Enrollment will be conducted by the study coordinators who will enter patient information directly into the Way to Health platform once a participant has consented to participate. This database is hosted on a secure server as detailed in the subject confidentiality section. Study coordinators may have to contact patients in the intervention and their support partners during the course of the study and will use the WTH database to access contact information to facilitate this contact. If suicidal ideation, is exhibited through text message or via PHQ-9 question 9 or DSM-5 Question 11. PHQ-9, Question 9 asks about thoughts of being better off dead or of hurting oneself in some way over the last two weeks with an associated scale delineating not at all, several days, more than half the days, or nearly every day. The DSM-5, question 11 asks about During the past TWO (2) WEEKS, how much (or how often) have you been bothered by the following problems? Thoughts of actually hurting yourself? with an associated scale delineating None: Not at all; Slight Rare, less than a day or two; Mild: Several days; Moderate: More than half the days; and Severe: Nearly every day. Those indicating any response beyond not at all or none not at all will be triaged to Penn Behavioral Health Corporate Services / EAP. This is the current standard of care and will be the same for both Cobalt and Cobalt plus in this trial. In case Penn Behavioral Health Corporate Services / EAP is unable to contact a study participant within the 72-hour period, a research team member will call the study participant and complete the Ask Suicide-Screening Questions (ASQ) and NIMH TOOLKIT: OUTPATIENT Brief Suicide Safety Assessment. This will be explained to the participant in the consent process and when the details of study participation are explained by the coordinator. If a participant books an appointment at the TEAMS Clinic, the research team will receive data from their PennChart such as if appointments are fulfilled or cancelled/skipped. Survey data will be submitted to the National Institute of Mental Health Data Archive (NDA) at the National Institutes of Health (NIH). NDA is a large database where deidentified study data from many NIH studies are stored and managed. De- identified study data means that all personal information (such as name, address, birthdate and phone number) is removed and replaced with a code number. PHI will not be shared with anyone outside the parameters of the study as detailed in the Consent/HIPAA process.

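### The scripted weekend auto-reply points to no help, although the plan itself names text messages as a route by which suicidal ideation may appear

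*Combined protocol and SAP*

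**What the plan says.** Section 10 (Subject Confidentiality) of the final protocol sets the hours of the Way to Health text line: "The research team is instructed to review the message within 1-4 hours of delivery, Monday through Friday, 8 am to 5pm". It then says: "The line will be closed on Saturday and Sunday however patient participants will receive an out of office message if they text in". The message is given as "Thank you for reaching out, we will get back to you when we get back in the office", "and a Patient Inquiry Incident is created". The first protocol in the combined document carries the same reply in its own Subject Confidentiality section.

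The sentence that follows in the final protocol reads, in part: "An exception to confidentiality is if significant suicidal ideation, is exhibited through text message or via PHQ-9 question 9". Section 10.1 (Subject Privacy) names the same route again: "If suicidal ideation, is exhibited through text message or via PHQ-9 question 9 or DSM-5 Question 11".

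Both sections then describe triage. Any positive answer to the self-harm items goes to the EAP. If the EAP cannot reach the person within 72 hours, a study team member calls and completes a suicide screen (the ASQ) and a brief safety assessment. On explaining this to participants, section 10.1 says: "This will be explained to the participant in the consent process and when the details of study participation are explained by the coordinator".

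Participants also agree at consent that "they will not disclose personal health information (PHI) on the Way to Health texting platform and only respond to the text" prompts.

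**The concern.** The plan foresees that a participant may express suicidal thoughts by text, and it fixes what that participant will read if the text is sent on a Saturday or Sunday. As quoted, the reply thanks the sender and promises contact later. It does not say that nobody is expected to read the message before Monday, and it gives no EAP contact, crisis line, Cobalt link or emergency instruction.

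This is a stated procedure that serves the participant poorly if it is followed. It is more than an omitted detail. A person in distress could take the reply to mean that someone has the message in hand. What is at stake is participant safety in both arms. The estimand, sample size and error rates are not involved.

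**Working it through.** The plan gives no figure on this point, so there is none to reproduce. The check is a reading of the text plus arithmetic on the stated hours.

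**Does any other safeguard put a pointer in front of the sender when the reply arrives?**

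| Safeguard (final protocol) | Who it reaches, and when |
|---|---|
| Immediate email notification (section 10) | Staff. The only stated duty to review is on weekdays, 8 am to 5 pm |
| Incident record (section 10) | Staff. No weekend reviewer or on-call person is named |
| EAP triage (sections 10 and 10.1) | The participant, but later. Its trigger is worded for questionnaire answers |
| Call with ASQ and safety assessment (sections 10 and 10.1) | The participant, after the EAP has failed to make contact within 72 hours |
| Explanation at consent (section 10.1) | The participant, at enrolment |
| Access to Cobalt, with monthly links in the intervention arm (section 6.3) | The participant, but the access must be self-initiated and the links are not tied to the text |
| Agreement to answer only prompts (section 10) | Makes such texts less likely, but the plan still lists text as a route |

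None of these changes what the sender reads when the reply arrives.

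**How long is the wait until staffed hours?** Inputs from section 10: review Monday to Friday, 8 am to 5 pm; line closed Saturday and Sunday; review target 1 to 4 hours. A week has 7 × 24 = 168 hours.

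- Staffed review: 5 × 9 = 45 h; 45/168 = 27%.
- Scripted reply in force: 2 × 24 = 48 h; 48/168 = 29%.
- Weekday hours outside 8 am to 5 pm: 5 × 24 − 45 = 75 h; 75/168 = 45%. The documents describe neither review nor a reply for these hours.
- Longest wait under the scripted reply, Saturday 00:00 to Monday 08:00: 24 + 24 + 8 = 56 h.
- Shortest wait under the scripted reply, end of Sunday to Monday 08:00: 8 h.
- Friday 17:00 to Monday 08:00: 7 + 48 + 8 = 63 h.
- Adding the review target to the Friday case: 63 + 1 = 64 h to 63 + 4 = 67 h.

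These are times until the instructed review period begins (or, in the last line, until review is due). They do not show that nobody looks sooner. The documents give no rate of suicidal texts, so no number of affected participants can be derived.

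**The case against.** The strongest case on the other side is that the decisive material may lie outside these documents. Consent pages were not available, section 10.1 promises an explanation of the suicidal-ideation process at consent, and section 8.1 promises a Manual of Operations. Either could tell participants that the line is unmonitored and whom to call. The quoted reply may also not be the complete live message. This stands as a limit on certainty. It does not answer the point, because an explanation at enrolment does not replace a pointer at the time of need.

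A second argument is that the sentence on text messages sets an exception to confidentiality and does not make the line a help channel. That is a fair reading of its purpose, but the sentence still shows that the route was foreseen. Section 10.1 can also be read as bringing texted ideation into the EAP and ASQ sequence. The sentence there is incomplete, so this is unclear. Even on that reading, the sequence starts after staff have seen the text.

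Third, the hours measure staffing, which a new message would not shorten. This is correct. They show how long the reply leaves a sender without direction. The 75 weekday hours rest on silence in the documents, which is not proof that no reply is sent.

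Fourth, the change has side effects. Routine out-of-hours replies to prompts would also trigger the message, and controls who text in would receive an EAP contact in a trial that compares pushed with pulled support. Both effects are small. Triage to the EAP is already the same in both arms, and the reply would be identical in each.

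**Conclusion.** The concern holds. Used as quoted, the weekend reply answers a foreseen suicidal text with a promise of later contact and nothing else. It applies for 48 of 168 hours a week, with 8 to 56 hours until staffed hours begin. For a text sent just after closing on Friday the wait is about 63 hours, although the documents do not say what reply, if any, is sent on Friday evening.

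The conclusion assumes that the protocol quotes the live message in full and that no more complete message is sent. Consent materials may list crisis contacts; that would lessen the gap without closing it. Frequency is unknown and probably low, and the planned comparison of PHQ-9 and GAD-7 at 6 months does not change. The possible harm is grave and the remedy is cheap, so the change should be made. Confidence is medium because of the unseen material.

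**What to change.** Replace the scripted reply in section 10 with one along these lines, with the wording settled by the study clinicians and the IRB:

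> This line is not monitored right now and is not for emergencies. If you are thinking of harming yourself or need support now, please contact [EAP contact] or [crisis line or emergency services]. For anything else, we will reply during office hours, Monday to Friday, 8 am to 5 pm.

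The study team must supply the contacts, since the copy available for review prints none. Send the message automatically, in both arms, at all times outside Monday to Friday, 8 am to 5 pm, and state in section 10 that it is sent on weekday evenings and nights too. The triage rule stays as it is.

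The cost is one edited template, a sending schedule on the texting platform and a short IRB modification, with no added staff. If the live message already carries these contacts at all those times, only the quotation in the protocol needs correcting.

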### 10.1 *Subject Privacy*

Aim 2 transcripts and audio files will be saved on a Penn Medicine managed, HIPAA compliant server. Interview audio-recordings will be transcribed verbatim and all identifiers will be removed. The recording and transcript will be kept a secure and locked area with access limited to designated researchers. After we analyze the recordings, we will destroy recordings after data analysis or completion of the study. All encounters will take place online via BlueJeans or Way to Health, HIPAA compliant platform. All encounters will take place in-person in a secure private room or online via Zoom (other Penn approved video conferencing platform) or Way to Health, HIPAA compliant platform. When utilizing Zoom for audio recordings, additional steps will be made by the research team to ensure participant safety. Based on guidelines, researchers will ensure the following settings for privacy and compliance for Penn Zoom. 1) Researchers will turn off the Personal Meeting ID setting and instead opt for the meeting ID to be generated automatically, allowing for new links and meeting IDs to be created for each meeting. 2) Research staff will turn off Cloud Recordings and ensure only local recordings that are HIPAA compliant are used as they are encrypted and managed by PMACS/DART or UPHS. Interview audio-recordings will be transcribed verbatim and all identifiers will be removed. The recording and transcript will be kept a secure and locked area with access limited to designated researchers. After we analyze the recordings, we will destroy recordings after data analysis or completion of the study. All survey data will be stored in a secure, web-based database (Way to Health or REDCap) where a study ID number will be generated for each patient. A link between the study ID number and the patient PHI will need to be maintained to ensure that the study staff can track recruitment efforts to potential participants and to avoid contacting any patients who have previously declined to participate. To ensure that patient confidentiality is preserved, individual identifiers (such as name) are stored in a single password protected system that is accessible to study research, analysis and IT staff only. This system is hosted on site at UPenn and is protected by a secure firewall. Once a participant is in this system, they will be given a unique study ID number. Any datasets and computer

## Effect of a Digital Engagement Strategy on Healthcare Worker Mental Health and Well-being: A Randomized Controlled Trial

files that leave the firewall will be stripped of all identifiers besides the study ID and individuals will be referred to by their study ID only. The study ID will also be used on all analytical files. Way to Health and REDCap are secure web applications for building and managing online surveys and databases. Privacy of all study data will be maintained by restricting access to the identifiable information only to approved study staff who have received subject confidentiality and privacy training. Study coordinators will access patient contact information from the database to conduct recruitment phone calls. The study coordinator will review the consent script, which will include a description of the voluntary nature of participation, the study procedures, risks and potential benefits in detail. Participants will be told that all information will be kept strictly confidential, except as required by law. Subjects will be provided a copy of the consent document. All efforts will be made by study staff to ensure subject privacy. Enrollment will be conducted by the study coordinators who will enter patient information directly into the Way to Health platform once a participant has consented to participate. This database is hosted on a secure server as detailed in the subject confidentiality section. Study coordinators may have to contact patients in the intervention and their support partners during the course of the study and will use the WTH database to access contact information to facilitate this contact. If suicidal ideation, is exhibited through text message or via PHQ-9 question 9 or DSM-5 Question 11. PHQ-9, Question 9 asks about thoughts of being better off dead or of hurting oneself in some way over the last two weeks with an associated scale delineating not at all, several days, more than half the days, or nearly every day. The DSM-5, question 11 asks about During the past TWO (2) WEEKS, how much (or how often) have you been bothered by the following problems? Thoughts of actually hurting yourself? with an associated scale delineating None: Not at all; Slight Rare, less than a day or two; Mild: Several days; Moderate: More than half the days; and Severe: Nearly every day. Those indicating any response beyond not at all or none not at all will be triaged to Penn Behavioral Health Corporate Services / EAP. This is the current standard of care and will be the same for both Cobalt and Cobalt plus in this trial. In case Penn Behavioral Health Corporate Services / EAP is unable to contact a study participant within the 72-hour period, a research team member will call the study participant and complete the Ask Suicide-Screening Questions (ASQ) and NIMH TOOLKIT: OUTPATIENT Brief Suicide Safety Assessment. This will be explained to the participant in the consent process and when the details of study participation are explained by the coordinator. If a participant books an appointment at the TEAMS Clinic, the research team will receive data from their PennChart such as if appointments are fulfilled or cancelled/skipped. Survey data will be submitted to the National Institute of Mental Health Data Archive (NDA) at the National Institutes of Health (NIH). NDA is a large database where deidentified study data from many NIH studies are stored and managed. De- identified study data means that all personal information (such as name, address, birthdate and phone number) is removed and replaced with a code number. PHI will not be shared with anyone outside the parameters of the study as detailed in the Consent/HIPAA process.

### 10.2 *Data Disclosure*

Survey data will be submitted to the National Institute of Mental Health Data Archive (NDA) at the National Institutes of Health (NIH). NDA is a large database where deidentified study data from many NIH studies are stored and managed. De- identified study data means that all personal information (such as name, address, birthdate and phone number) is removed and replaced with a code number. PHI will not be shared with anyone outside the parameters of the study as detailed in the Consent/HIPAA process.

### 10.3 *Data confidentiality*

The following methods will be employed to protect patient PHI for this research study:

Effect of a Digital Engagement Strategy on Healthcare Worker Mental Health and Well-being: A Randomized Controlled Trial

- x Computer-based files will only be made available to personnel involved in the study through the use of access privileges and passwords.
- x Prior to access to any study-related information, personnel will be required to sign statements agreeing to protect the security and confidentiality of identifiable information.
- x Wherever feasible, identifiers will be removed from study-related information.
- x A Certificate of Confidentiality will be obtained, because the research could place the subject at risk of criminal or civil liability or cause damage to the subject's financial standing, employability, or liability.
- x Precautions are in place to ensure the data is secure by using passwords and encryption, because the research involves web-based surveys.
- x Audio and/or video recordings will be transcribed and then destroyed to eliminate audible identification of subjects.

## 11. Consent Process Overview

Participants will enroll in this study via a remote recruitment process. The study coordinator will review the consent script, which will include a description of the voluntary nature of participation, the study procedures, risks and potential benefits in detail. Participants will be told that all information will be kept strictly confidential, except as required by law. Subjects will be provided a copy of the consent document. All efforts will be made by study staff to ensure subject privacy. Enrollment will be conducted by the study coordinators who will enter patient information directly into the Way to Health platform once a participant has consented to participate.

### 11.1 *Potential Study Risks*

We are requesting a waiver of the requirement to document consent and HIPAA authorization with a signature for participants enrolled into this study since we believe that the research presents no more than minimal risk of harm to subjects and involves no procedures for which written consent is normally required outside of the research context. [45 CFR 46.117(c)(2)] Participants will enroll in this study via a remote recruitment process, and therefore, we will read the IRB-approved Consent/HIPAA script over the phone to each participant and ask them to provide verbal consent and verbal HIPAA authorization for use of their data in the study. After a patient provides verbal consent, the coordinator will select this option on the Consent/HIPAA screen on the participants' profile that was created during enrollment on the WTH platform for this study. A copy of the Consent/HIPAA document will be included in the device packet provided to them by mail to the patients' home address.

